5.8.3 Other secondary/exploratory analysis

Kaplan-Meier estimates

An estimate of the survival function in each treatment group will be constructed using Kaplan-Meier (product-limit) method as implemented in PROC LIFETEST with METHOD=KM option. The PROC LIFETEST statement will use the option CONFTYPE=LOGLOG.

Median survival for each treatment group will be obtained along with 95% confidence intervals calculated from PROC LIFETEST output using the method of ([Brookmeyer, Crowley 1982](#)). Kaplan-Meier estimates of the survivor function with 95% confidence intervals at specific time points will be summarized. The standard error of the Kaplan-Meier estimate will be calculated using Greenwood's formula ([Collett 1994](#)).

Difference in survival rate using log-rank test

Between treatment difference will be evaluated using a log-rank test from PROC LIFETEST with STRATA <treatment> with test=logrank option and TEST <treatment> statements. For pooled time to event data from cohort 1 and 2, stratified log-rank test will be performed using STRATA <cohort> statement with GROUP = <treatment> option.

Confidence interval for geometric mean ratio

For PK parameters, such as AUC_{0-24h} , C_{max} , the values for individuals will be converted into \log_e scale. Mean and corresponding 2-sided $100 \times (1-\alpha)\%$ confidence intervals (CI) will be calculated using PROC TTEST by assuming normality of data on log scale. The geometric mean, the lower and upper confidence limits will be calculated by exponentiating the arithmetic means, and lower and upper confidence limit that were derived using log data.

5.8.4 Sensitivity analysis for between treatment difference in clinical success using multiple imputation

The difference in clinical success between the two treatment groups at different visits (24 hours, 48 hours, 72 hours, hospital discharge , Day 6, Day 8, Day 15, Day 22, and Day 29) will be evaluated using Wilson's uncorrected method for individual cohorts and Mantel-Haenszel estimate for pooled cohorts as described in [Section 2.7](#) with multiple imputations as sensitivity analysis for missing clinical endpoint not due to death related to malaria (missing due to death not related malaria or missing due to lost to followup) after the hospital discharge and discontinuation of study.

The feasibility of following plan will be tested using blinded data at CSR dryrun and may be revised later if necessary.

Clinical success is a dichotomous composite (comprised of malaria related death, *P. falciparum* asexual parasites count, and major clinical signs of severe malaria) variable which is derived according to [Section 2.1.1](#) and restated below.

A patient is said to have achieved the clinical success at a given timepoint if the patient did not die either during the initial hospitalization nor due to malaria post the initial hospitalization, shows absence of *P. falciparum* asexual parasites (using local lab for all cohorts and repeated for central lab for Cohorts 1 and 2), and did not have any of the key signs or symptoms of severe malaria on that given timepoint. Note: Deaths occurring post initial hospitalization will be evaluated by designated adjudication committee to confirm if they are related to malaria.

In the current study, Blood film for microscopic counts of *P. falciparum* asexual parasite are collected at screening, pre-dose, Hours 1, 2, 4, 6, 12, 18, 24, 30, 36, 42, 48, 72 (hospital discharge), Days 6, 8, 15, 22, 29, and unscheduled visit. Neurological assessments are performed on screening, pre-dose, Hours 6, 12, 18, 24, 36, 48, 72 (hospital discharge), Days 6, 8, 15, 22, 29, and unscheduled visit. Altered consciousness will be determined using these neurological assessments as defined in [Section 2.1.1](#). Plasma lactate and serum creatinine assessments are performed on screening, Hours 6, 12, 18, 24, 36, 48, 72 (hospital discharge), Days 6, 8, 15, 22, 29, and unscheduled visit. Note: if hospital discharge does not occur at Hour 72 or a scheduled visit, these assessments should be performed at hospital discharge. Renal replacement therapy (RRT) will be captured on concomitant and non-drug therapy CRF page. These assessments are required for determination of renal impairment. Respiratory distress is recorded by investigator in the severe malaria CRF and will also be identified using adverse event pages.

Key signs of Severe Malaria are (a) Altered consciousness, (b) Renal impairment, (c) Acidosis. These signs are defined below.

Altered consciousness – Prostration (inability to sit or drink or breast feed) or GCS < 11 for patients > 5 years / BCS < 3 for patients ≤ 5 years of age. Prostration, GCS/ BCS is recorded by investigator in the relevant CRF. In case that a patient completes the visit but the data are missing, this will be determined to be ‘yes’ if a patient has an AE of “Altered state of consciousness” with starting day since previous visit to the current visit and ‘no’ otherwise.

Renal Impairment - Serum creatinine > 3xULN or > 3 mg/dL or need for renal replacement therapy (RRT). Serum creatinine is recorded in the point of care devices (POC) or using local lab in case of non-availability of POC and renal replacement is recorded by investigator in the concomitant CRF. In case that a patient completes the visit but the serum creatinine is missing, this will be determined to be ‘yes’ if a patient has an “renal replacement” concomitant with starting day since previous visit to the current visit and ‘no’ otherwise.

Acidosis - Plasma lactate ≥ 4 mmol/L (In database, lactate is captured under lactic acid) or Respiratory distress. Plasma lactate is recorded in the point of care devices (POC) or using local lab in case of non-availability of POC and respiratory distress is recorded by investigator in the severe malaria CRF. In case that a patient completes the visit but the data are missing, this will be determined to be ‘yes’ if a patient has an AE of “Respiratory distress” with starting day since previous visit to the current visit and ‘no’ otherwise.

Single imputation rule:

Following single imputations will be performed before applying the multiple imputations:

After a patient has parasite clearance, any intermediate missing parasite between 2 negative parasite assessments is imputed as negative parasite assessment since it is very likely that the intermediate missing should also be negative as prior and post missing data show negative result.

Once a patient died before hospital discharge or is declared as malaria related death at a timepoint, the patient will be considered as not achieving the clinical success for the timepoint onwards.

If a patient has parasite reappearance after the hospital discharge, the patient is considered as not achieving the clinical success for the timepoint onwards.

If a patient receives IV antimalarial rescue medication prior to hospital discharge, the patient is considered as not achieving the clinical success for the timepoint onwards.

Other imputations that are specified in the previous sections will be performed prior to multiple imputation.

Assumptions considered

Since the parasite count data is usually skewed ([N Alexander 2012](#)), it is assumed to follow log-normal distribution.

Since the control is standard of care (SoC), data from control group should not be used to impute the missing data for the test group and vice versa to avoid the potential bias. Therefore, imputation technique such as 'Jump to reference' or 'Copy to reference' cannot be used since under these techniques, model uses the data from the reference group while imputing the missing values in the test group and vice versa. Instead, for each treatment group, missing values will be imputed separately using missing at random (MAR) assumption ([Carpenter, Kenward 2013](#)). Also, since the patients will be remained hospitalized during the IV treatment period, there is a less chance of missing on-treatment data.

The 0 parasite counts (below assay detection limit) will be first imputed with the detection limit before transforming into the log since log does not exist for 0.

Description of MI procedure

Multiple imputation (MI) is a simulation based approach where missing values are replaced by multiple Bayesian draws from the conditional distribution of missing data given the observed data and covariates, creating multiple completed data sets. These completed data sets can then be analyzed using standard methods and software for balanced data. ([Rubin \(1987\)](#)) presented rules how to combine the multiple sets of estimates to produce overall estimates and confidence intervals that adequately incorporate missing data uncertainty.

FCS method

Fully conditional specification (FCS) method is used to impute the missing data. FCS method uses a separate conditional distribution for each imputed variable. The FCS statement uses a multivariate imputation by chained equations method to impute values for a data set with an arbitrary missing pattern, assuming a joint distribution exists for the data. A FCS method does

not start with an explicitly specified multivariate distribution for all variables, but rather uses a separate conditional distribution for each imputed variable. For each imputation, the process contains two phases: the preliminary filled-in phase followed by the imputation phase. At the filled-in phase, the missing values for all variables are filled in sequentially over the variables taken one at a time. These filled-in values provide starting values for these missing values at the imputation phase. At the imputation phase, the missing values for each variable are imputed sequentially for a number of burn-in iterations before the imputation.

For continuous variables, a regression method; and for dichotomous variables, a discriminant function method is used to impute missing values.

MI model for Clinical success

Since the clinical success is a composite variable, based on individual signs of severe malaria renal impairment, acidosis, prostration, these individual variables collected before Hours 24 will also be included in the multiple imputation model along with the parasite data while imputing clinical success at Hours 24, which is the first timepoint at which the clinical success is being evaluated.

For the imputation of clinical success at 48 hour, individual signs of severe malaria before 24 hours and at 36 hours will be included but not at the 24 hours in the imputation model. Instead, clinical success at 24 hours will be included in the model. Individual signs at Hours 24 is not included because clinical success at 24 hours is based on the individual signs at Hours 24. The individual signs at 48 hours will also not be included because if the clinical success at Hour 48 is missing then the individual signs will also be missing and hence there is no gain in including these variables in the model, which will unnecessarily increase the burden on the imputation model. Similar approach will be used for the imputation of clinical success at other visits.

Among the following variables, different sets of variables will be used for multiple imputation model depending on which timepoint is concerned- Baseline weight, age, country, log-parasites counts for initial infection (from baseline upto Hours 18 for KAE609 and from baseline upto Hours 48 for artesunate), presence of parasitaemia (yes/no) (post 18 hours for KAE609, post 48 hours for artesunate), altered consciousness (yes/no) at each visit, renal impairment (yes/no) at each visit, acidosis (yes/no) at each visit, respiratory distress (yes/no) at each visit, and clinical success at each visit. Dichotomous variable of existence of parasites after 24 hours for KAE609 and 48 hours for artesunate is considered instead of log-count itself because it is more likely that initial parasites will be disappeared by then resulting into 0 counts for patients treated with KAE609 and artesunate respectively.

Since hospital discharge may be at different timepoint for different patients, it's not possible to provide the fixed number of covariates for imputation of clinical success at discharge. Also, it is expected that most of the patients will be discharged by 72 hours, and this timepoint is considered for the multiple imputation.

The missing values at a particular time point will be imputed using the data prior to that time point only along with other demographic variables. E.g. missing value at 48 hours will be imputed using the data available prior to 48 hours but not using the later timepoint. Clinically, it makes sense to use earlier data to predict the future outcome. This will be controlled by

defining a separate FCS statement for each individual variable, for which the missing values are to be imputed. Data at study discontinuation visit or unscheduled visits will be mapped to the planned visit as per the visit-mapping window.

It has been observed in the Phase II study of oral KAE609 formulation for uncomplicated malaria that the most patients have achieved parasite clearance by 24 hours. This implies that post 24 hours results may be negative for all KAE609 patients, which results into a constant value for all the patients. For artesunate, the median parasite clearance time is expected to be >40 hours. Therefore, post 48 hours, results may be negative for all artesunate patients, which results into a constant value for all the patients. In such cases, variables with constant value will be dropped from imputation model, otherwise, SAS procedure, PROC MI will fail with error.

Clinical success at different visits will be imputed using discriminant function by FCS method. The imputations will be done separately for each treatment group. The number of imputations will be set to 100; the seed for the random function will be set to 60912201 for this study.

To generate the multiple imputed data sets, the SAS procedure MI can be used as follows:

The input data set <CLNSUC_dd> should have one record per patient with country, age, baseline weight, gender, log (parasite counts) from baseline up to 18 hours for KAE (and up to 48 hours for artesunate), parasitaemia status from 24 to 72 hours (presence/absence) for each visit for KAE609 (72 hours for artesunate), altered consciousness (yes/no) at each visit, renal impairment (yes/no) at each visit, acidosis (yes/no) at each visit, and clinical success (yes/no) at each visit.

Two outputs will be prepared displaying i) the missing data patterns and the group means as stored in the data set msgpat and ii) the variance information and estimated means with confidence interval and range based on data sets varinfo and param which need to be merged by <treatment group> and <variable>.

The imputed data are saved in data set <impdata>.

For each of the completed dataset, clinical success will be derived according the definition in [Section 2.1.1](#). The percentage of patients with clinical success (\hat{P}) at different timepoints such as 24 hours, 48 hours, 72 hours, hospital discharge, Day 6, Day 8, Day 15, Day 22, and Day 29 will be calculated as $n/N \times 100\%$ for each treatment group and for each of the complete datasets; where n =no. of patients with clinical success and N =no. of patients in FAS.

Combining clinical success rates and 90%CI for each treatment group

Results from the imputation model will be used to estimate the combined clinical success rates and associated 90%CIs.

[Rubin \(1987\)](#) presented rules how to combine the multiple sets of estimates to produce overall estimates and confidence intervals that adequately incorporate missing data uncertainty.

Following this, average estimate of clinical success rate (P) from m completed datasets will be calculated as $\bar{P}_m = \frac{\sum \hat{P}_i}{m}$, where \hat{P}_i is the estimate of P from i^{th} completed dataset.

Estimate of the pooled variance of the m completed dataset is $T_m = \left(1 + \frac{1}{m}\right) B_m + \overline{U}_m$, where $B_m = \frac{\sum (\hat{P}_i - \overline{P}_m)^2}{m-1}$ (between variance) and $\overline{U}_m = \frac{\sum \hat{U}_i}{m}$ (within imputation variance), $\hat{U}_i = \frac{\hat{P}_i(1-\hat{P}_i)}{n}$. 90% CI for the P will be derived based on Wilson uncorrected method using multiple imputed datasets (MI-Wilson) described by Anne, as follows.

Let t be the quantile of the t_v distribution with the confidence level $1-\alpha$ such that

$$P\left(-t \leq \frac{\overline{P}_m - \overline{P}_m}{\sqrt{T_m}} \leq t\right) = 1-\alpha \text{Eq (1),}$$

where $v = (m-1)\left(1 + \frac{1}{r_m}\right)^2$, and $r_m = \left(1 + \frac{1}{m}\right) B_m / \overline{U}_m$

Substituting the expression for T_m and squaring the terms inside the above probability expression of equation (1) will lead the quadratic equation for P. Solving the quadratic equation for P, two limits (MI-Wilson) will be obtained as follows.

$$\frac{2\overline{P}_m + \frac{t^2}{n} + \frac{t^2 r_m}{n}}{2\left(1 + \frac{t^2}{n} + \frac{t^2 r_m}{n}\right)} \pm \text{sqrt}\left[\frac{\left(2\overline{P}_m + \frac{t^2}{n} + \frac{t^2 r_m}{n}\right)^2}{4\left(1 + \frac{t^2}{n} + \frac{t^2 r_m}{n}\right)^2} - \frac{\overline{P}_m^2}{1 + \frac{t^2}{n} + \frac{t^2 r_m}{n}}\right] \text{Eq (2)}$$

It may be possible that $B_m = 0$ or $B_m = \overline{U}_m = 0$ leading r_m to be undefined. In this case set $r_m = 0$ with $v=\infty$ ([Anne, Jerome 2018](#)). Note: a t-distribution with ∞ degree of freedom is the standard normal distribution.

As the MIANALYZE procedure expects the parameter estimate in the variables ESTIMATE, and the corresponding standard error in the variable STDERR whereas the MI-Wilson procedure works on solving quadratic equation, MIANALYZE procedure can not be used to combine the 90% CIs for multiple imputations, however, it can still be used to obtain the combined point estimate, \overline{P}_m . For 90% CIs, equation (2) will be used.

Between treatment difference and 90% CI in combined clinical success rates based on MI

After obtaining the individual estimates of clinical success rates and the 90% CIs for each treatment group, the between treatment difference and the corresponding 90% CI for the difference will be calculated as described in [Newcombe 1998](#).

Let \overline{P}_{m1} and \overline{P}_{m2} be the average estimate of clinical success rates, L_{m1} and L_{m2} be the lower confidence limits, and U_{m1} and U_{m2} be the upper confidence limits based on the multiple imputed datasets for the test group and control group, respectively,

Then the Newcombe confidence limits for the difference in clinical success rates, $D_m = \overline{P}_{m1} - \overline{P}_{m2}$ is

$$D_{mL} = D_m - \sqrt{(\overline{P}_{m1} - L_{m1})^2 + (U_{m2} - \overline{P}_{m2})^2}$$

$$D_{mU} = D_m + \sqrt{(U_{m1} - \overline{P}_{m1})^2 + (\overline{P}_{m2} - L_{m2})^2}$$

Example SAS code

#Note: The following codes is written to impute clinical success at hours 24, 48, 72, Days 6, 8, 15, 22 and Day 29 for KAE609.

#Since hospital discharge is at different timepoint for different patients, its not considered for the imputation since its not feasible to provide the fixed number of covariates for imputation of clinical success at discharge.

In general, these items are missing altogether if a patient misses a visit. If a patient does not miss a visit, missing individual item should be minimal.

The following are the convention for variable naming:

- Suffix after '_' indicates timing, ||B= means baseline, H36 means 36 hours posting dosing, D15 means at Day 15, etc.
- Prefix 'par': means dichotomous parasite count (absent or presence)
- Prefix ||ln=: means log parasite count (continuous)
- Prefix ||CLSUC=: means clinical success (yes or no)
- Prefix ||REN=: means renal impairment (yes/no)
- Prefix ||ACID=: means acidosis (yes/no)
- Prefix ||ALTCON=: means altered consciousness (yes/no)

```
ODS LISTING CLOSE;
```

```
ODS OUTPUT MissPattern=msgpat VarianceInfo=varinfo
```

```
ParameterEstimates=param;
```

```
/*FOR KAE609*/
```

```
proc mi data= <CLINSUC_dd> seed=2201 nimpute=&nimp out=  
clinsuc_mi;
```

```
    where trt01p==KAE609=; *Imputation within treatment;
```

```
class COUNTRY gender par_h24 par_h36 par_h48 par_h72  
CLSUC_h24 CLSUC_h48 CLSUC_h72 CLSUC_D6 CLSUC_D8 CLSUC_D15  
CLSUC_D22 CLSUC_D29 REN_B REN_H6 REN_H12 REN_H18 ACID_B  
ACID_H6 ACID_H12 ACID_H18
```

ALTCON_B ALTCON_H6 ALTCON_H12 ALTCON_H18;*put all categorical variables upto 24 hours since they are needed to impute clinical response at 24 hours;

```
fcs discrim (CLSUC_h24 = COUNTRY age gender ln_s ln_b ln_h1  
ln_h2 ln_h4 ln_h6 ln_h12 ln_h18 REN_B REN_H6 REN_H12 REN_H18  
ACID_B ACID_H6 ACID_H12 ACID_H18 ALTCON_B ALTCON_H6 ALTCON_H12  
ALTCON_H18 )
```

```
fcs discrim (CLSUC_48 = COUNTRY age gender ln_s ln_b ln_h1  
ln_h2 ln_h4 ln_h6 ln_h12 ln_h18 par_h24 par_h36 REN_B REN_H6  
REN_H12 REN_H18 REN_H36 ACID_B ACID_H6 ACID_H12 ACID_H18  
ACID_H36 ALTCON_B ALTCON_H6 ALTCON_H12 ALTCON_H18 ALTCON_H36  
CLSUC_h24)
```

```
fcs discrim ( CLSUC_h72 = COUNTRY age gender ln_s ln_b ln_h1  
ln_h2 ln_h4 ln_h6 ln_h12 ln_h18 par_h24 par_h36 par_h48  
REN_B REN_H6 REN_H12 REN_H18 REN_H36 ACID_B ACID_H6 ACID_H12  
ACID_H18 ACID_H36 ALTCON_B ALTCON_H6 ALTCON_H12 ALTCON_H18  
ALTCON_H36 CLSUC_h24 CLSUC_h48)
```

```
fcs discrim ( CLSUC_D6 = COUNTRY age gender ln_s ln_b ln_h1  
ln_h2 ln_h4 ln_h6 ln_h12 ln_h18 par_h24 par_h36 par_h48  
par_h72 REN_B REN_H6 REN_H12 REN_H18 REN_H36 ACID_B ACID_H6  
ACID_H12 ACID_H18 ACID_H36 ALTCON_B ALTCON_H6 ALTCON_H12  
ALTCON_H18 ALTCON_H36 CLSUC_h24 CLSUC_h48 CLSUC_h72  
)
```

```
fcs discrim ( CLSUC_D8 = COUNTRY age gender ln_s ln_b ln_h1  
ln_h2 ln_h4 ln_h6 ln_h12 ln_h18 par_h24 par_h36 par_h48  
par_h72 REN_B REN_H6 REN_H12 REN_H18 REN_H36 ACID_B ACID_H6  
ACID_H12 ACID_H18 ACID_H36 ALTCON_B ALTCON_H6 ALTCON_H12  
ALTCON_H18 ALTCON_H36 CLSUC_h24 CLSUC_h48 CLSUC_h72 CLSUC_D6  
)
```

```
fcs discrim ( CLSUC_D15 = COUNTRY age gender ln_s ln_b ln_h1  
ln_h2 ln_h4 ln_h6 ln_h12 ln_h18 par_h24 par_h36 par_h48  
par_h72 REN_B REN_H6 REN_H12 REN_H18 REN_H36 ACID_B ACID_H6  
ACID_H12 ACID_H18 ACID_H36 ALTCON_B ALTCON_H6 ALTCON_H12
```

```
ALTCON_H18 ALTCON_H36 CLSUC_h24 CLSUC_h48 CLSUC_h72 CLSUC_D6  
CLSUC_D8  
)
```

```
fcs discrim ( CLSUC_D22 = COUNTRY age gender ln_s ln_b ln_h1  
ln_h2 ln_h4 ln_h6 ln_h12 ln_h18 par_h24 par_h36 par_h48  
par_h72 REN_B REN_H6 REN_H12 REN_H18 REN_H36 ACID_B ACID_H6  
ACID_H12 ACID_H18 ACID_H36 ALTCON_B ALTCON_H6 ALTCON_H12  
ALTCON_H18 ALTCON_H36 CLSUC_h24 CLSUC_h48 CLSUC_h72 CLSUC_D6  
CLSUC_D8 CLSUC_D15  
)
```

```
fcs discrim ( CLSUC_D29 = COUNTRY age gender ln_s ln_b ln_h1  
ln_h2 ln_h4 ln_h6 ln_h12 ln_h18 par_h24 par_h36 par_h48  
par_h72 REN_B REN_H6 REN_H12 REN_H18 REN_H36 ACID_B ACID_H6  
ACID_H12 ACID_H18 ACID_H36 ALTCON_B ALTCON_H6 ALTCON_H12  
ALTCON_H18 ALTCON_H36 CLSUC_h24 CLSUC_h48 CLSUC_h72 CLSUC_D6  
CLSUC_D8 CLSUC_D15 CLSUC_D22  
)
```

```
var COUNTRY age weight gender  
ln_s ln_b ln_h1 ln_h2 ln_h4 ln_h6 ln_h12 ln_h18 par_h24  
par_h36 par_h48 par_h72  
CLSUC_h24 CLSUC_h48 CLSUC_h72 CLSUC_D6 CLSUC_D8 CLSUC_D15  
CLSUC_D22 CLSUC_D29 REN_B REN_H6 REN_H12 REN_H18 REN_H24  
ACID_B ACID_H6 ACID_H12 ACID_H18 ACID_H24 ALTCON_B ALTCON_H6  
ALTCON_H12 ALTCON_H18 ALTCON_H24  
run;
```

```
ODS LISTING;
```

```
/*Artusunate*/
```

```
/*Similar code will be used for the imputation of clinical  
success for artesunate with the change of variables related to  
parasite count data such as- a). Delete par_h24, par_h36, and  
par_h48 from CLASS and VAR statement. b) Include ln_h24,  
ln_h36 and ln_h48 in VAR statement, and c) Replace par_h24,
```

par_h36, and par_h48 with ln_h24, ln_h36 and ln_h48 in FCS statements respectively */

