Time (post-dose)	-	0h ⁴	2m	10m	30m	1h	2h	4h	6h	12h	18h	24hm	24.02hm	25h	30h	36h	42h	48hm	48.02hm	49h	60h	72h
Informed consent ⁵	X																					
Inclusion / Exclusion criteria	X																					
Demography	X																					
Medical history/current medical conditions	X																					
Malaria Blood Film for parasite count and gametocyte count	X	X ⁶				X	X	X	X	X	X	X			X	X	X	X				X
Physical Examination	S								S	S	S	S				S		S				S
Neurological Examination	X								X	X	X	X				X		X				X
Other severe malaria examinations ⁸	X								X	X	X	X				X		X				X
Body Temperature	X	X			X				X	X	X	X				X		X				X
Vital Signs (blood pressure, pulse)	X	X			X				X	X	X	X				X		X				X
Blood chemistry - Point of Care device Hepatic Panel	X									X		X				X		X				X
Blood chemistry - Point of Care device, Met Lac Panel	X								X	X		X				X		X				X
Hematological assessment - Point of Care device	X									X		X				X		X				X
Blood chemistry (INR and LDH) at local lab ⁹		X ⁶																				
Electrocardiogram (ECG) ¹⁰		X ⁶										X ¹¹						X ¹¹				X ¹¹
PK Collection ¹²		X ⁶	X	X		X		X		X		X	X	X		X		X	X	X	X	X
Alpha 1-Acid glycoprotein (AAG) blood collection ¹³		X ⁶										X						X				
Urine analysis - local lab	X											X				X		X				X
CCI																						
CCI																						
CCI																						
CCI																						
CCI																						
CCI																						
Pregnancy Test (serum) ⁷	S																					
Body Height	X																					
Body Weight	X													X								
Administration of IV therapy - Cipargamin (KAE609) Or Artesunate ¹⁸		X								X ¹⁹		X						X				
Administration of Oral Therapy (standard of care) ²⁰																		X ²⁰				X ²⁰
Contact IRT	X	X										X						X				X
Adverse Events		Ongoing check																				
Prior and concomitant medications ²¹		As required																				

Period	Follow-up					Unscheduled visit
Visit Name	D6	D8	D15	D22	D29 (EOS/PSW) ²²	Unscheduled visit
Days	6	8	15±1	22±2	29±2	-
Time (post-dose)	120h	168h	336h	504h	672h	-
Informed consent ⁵						
Inclusion / Exclusion criteria						
Demography						
Medical history/current medical conditions						
Malaria Blood Film for parasite count and gametocyte count	x	x	x	x	x	x
Physical Examination ⁷	s	s	s	s	s	s
Neurological Examination	x	x	x	x	x	x
Other severe malaria examinations ⁸	x	x	x	x	x	x
Body Temperature	x	x	x	x	x	x
Vital Signs (blood pressure, pulse)	x	x	x	x	x	x
Blood chemistry - Point of Care device Hepatic Panel	x	x	x	x	x	x

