2.6.3 Handling of intercurrent events and missing data for secondary estimand

Handling of intercurrent events will be done according to [Table 2-2](#); and missing data not related to intercurrent events will be handled according to [Table 2-3](#).

Table 2-2 Handling of intercurrent events and other events that may occur and affect the derivation of secondary estimand

Event	Outcome
Receive IV antimalarial rescue medication prior to 48 hours	Not clinical success

Table 2-3 Handling of missing data that may occur and affect the derivation of secondary estimand

Reason for missing assessment	Method of imputation
Discontinue the study prior to 48 hours, such as withdrawal of consent, COVID-19, etc.	Not clinical success due to early discharge
Missing parasite assessment at 48 hours [§]	
• Not clinical success if asexual parasites present in the latest visit prior to 48 hours• Ignored* otherwise
Altered consciousness: missing Prostration, missing Glasgow Coma Score or missing Blantyre coma score in relevant age groups [§]	Use the result from the latest visit prior to 48 hours (including baseline) for each missing item
Renal impairment: missing SCr [§]	
• Not clinical success if Renal Replacement Therapy is used at 48 hours• Use the latest SCr prior to 48 hours
Acidosis and respiratory distress: missing plasma lactate or missing respiratory distress assessment [§]	Use the result from the latest visit prior to 48 hours (including baseline) for each missing item
* determination of clinical success depends on other assessments.	
[§] Partial data missing, unlikely since patients are in the hospital	

Note: partial data missing should be rare since patients are still hospitalized at 48 hours.

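### SAP 5.8.4 scores a missing sign at a completed visit as absent unless it newly began, in conflict with Tables 2-3 and 2-4, and it assumes 18 h chemistry that is not scheduled

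*SAP*

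**What the plan says.** SAP 5.8.4 gives a missing-item rule for each of the three key signs.

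- **Renal impairment.** The rule starts "In case that a patient completes the visit but the serum creatinine is missing". The sign is then *yes* only if there is a renal replacement record "concomitant with starting day since previous visit to the current visit", and *no* otherwise.
- **Altered consciousness and acidosis.** Both rules start "In case that a patient completes the visit but the data are missing". They look for an adverse event (AE) of altered state of consciousness, or of respiratory distress, with a start day in the same interval. Without one, the sign is *no*.

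The earlier sections treat the same gap differently. At 48 h, Table 2-3 says "Not clinical success if Renal Replacement Therapy is used at 48 hours" and otherwise takes the latest earlier creatinine. For the consciousness and acidosis items it says "Use the result from the latest visit prior to 48 hours (including baseline) for each missing item". The in-hospital column of Table 2-4 works the same way. Its post-discharge column counts certain AEs reported for the visit, or renal replacement used at the visit, as failure and otherwise ignores the missing item.

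On timing, 5.8.4 states "Plasma lactate and serum creatinine assessments are performed on screening, Hours 6, 12, 18, 24, 36, 48, 72 (hospital discharge", followed by the later visits. The example code uses "REN_B REN_H6 REN_H12 REN_H18" as covariates, with the matching acidosis variables.

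**The concern.** A multiple-imputation sensitivity analysis should differ from the main analysis only in how it treats the outcomes it imputes. SAP 2.7.2.1 calls for it for deaths not related to malaria and for discontinuation after hospital discharge. Section 5.8.4 also re-codes signs at visits that participants attended, and it does so by new onset rather than by presence. Someone whose coma, acidosis or renal replacement continues, but whose item is missing that day, becomes free of the sign.

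The re-coded signs act twice. They are predictors in the imputation models, and clinical success is derived again in each completed dataset. If the result then differs from the main one, the reader cannot tell whether the missing-data assumption or the changed derivation is responsible. The 18 h chemistry adds predictors presented as measured when they are not.

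**Working it through.** The plan states no figure to reproduce, so the check sets the rules side by side, compares the schedules, and then sizes one re-coded participant.

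**1. Same participant, two rules.** The cases are hypothetical, and each visit was completed.

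| Case | SAP 5.8.4 | Table 2-3 or 2-4 |
|---|---|---|
| (a) Coma from baseline to 18 h; consciousness items missing at 24 h; no new AE | absent | present (carried forward) |
| (b) Renal replacement begun on Day 1 and still running; previous visit at 36 h; creatinine missing at 48 h | absent | not clinical success |
| (c) Lactate 7 mmol/L at 36 h; lactate missing at 48 h; no new respiratory distress AE | absent | present (7 > 4, carried forward) |
| (d) Consciousness normal at 18 h; items missing at 24 h; AE of altered state of consciousness begun in between | present | absent (normal result carried forward) |
| (e) Renal replacement begun after the previous visit but stopped before this one; creatinine missing; latest creatinine below threshold | present | absent |
| (f) After discharge: prostration AE reported for the visit but begun before the previous visit; consciousness items missing | absent | not clinical success |

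Cases (a) to (c) and (f) move towards success; (d) and (e) move towards failure. In (b) the start falls on an earlier study day than the previous visit, so the result does not depend on whether clock times are recorded. Case (b) also conflicts with 5.8.4 itself, whose renal definition includes the need for renal replacement.

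**2. After discharge.** Two differences remain. Section 5.8.4 asks for onset since the last visit, whereas Table 2-4 asks whether the event was reported for, or used at, the visit. Table 2-4 also counts AEs of renal failure or impairment, lactic acidosis, prostration and coma, which 5.8.4 does not list. Both rules otherwise default to success on the missing item.

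**3. The 18 h samples.**

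- Protocol Tables 8-1 and 8-2, row "Blood chemistry - Point of Care device, Met Lac Panel": screening, 6, 12, 24, 36, 48 and 72 h during the hospital stay.
- Same tables, hepatic panel: screening, 12, 24, 36, 48 and 72 h.
- Same tables, neurological and other severe-malaria examinations: screening, 6, 12, **18**, 24, 36, 48 and 72 h.
- SAP Table 5-9, chemistry column: more than 9 to 18 h maps to the 12 h visit, more than 18 to 30 h maps to 24 h, and the 18 h row is NA.

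The documents do not say which panel contains creatinine, but neither is drawn at 18 h. Under the SAP's own windows even an unscheduled sample cannot fill that slot. REN_H18 is therefore missing by design and becomes *no* unless renal replacement began between 12 and 18 h. ACID_H18 can reflect respiratory distress only. For example, a participant with raised creatinine at both 12 h and 24 h, and no new renal replacement, is coded unimpaired at 18 h.

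**4. Size.** The planned evaluable number is 107 per pooled arm (SAP 3.2). One re-coded participant changes an arm's success rate by 1/107 = 0.93 percentage points, and five by 5/107 = 4.67. The documents do not give the number affected, so 1 to 5 is an assumed range. For scale, the planned half-width of the 90% interval for the difference is 10 points.

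**The case against.** The strongest reply is that 5.8.4 itself says the imputations from the previous sections are performed before multiple imputation. If Tables 2-3 and 2-4 run first, few in-hospital gaps are left for the 5.8.4 rules. This may be the intention, but the text gives no order between the two rule sets and states the 5.8.4 rules without qualification. A programmer could follow either.

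The same sentence answers a stronger reading. A reader might infer that 5.8.4 fails IV rescue only when it is given before discharge. The documents do not support that: 5.8.4 states a rule for rescue before discharge, without saying it is the only one, and brings in Table 2-4, which fails rescue before any visit.

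A reader might also infer that the change always favours success. Cases (d) and (e) show otherwise. Section 5.8.4 also prints the lactate criterion as at least 4 mmol/L, against above 4 in SAP 2.1.1, which is slightly stricter. The main direction is towards success only for signs already present.

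Three further points stand. This analysis chiefly targets the period after discharge, where the conflict is narrower. Clinical success is not evaluated at 18 h, and the SAP drops covariates that are constant, so a REN_H18 that is *no* for everyone would disappear. And the code is an example, in a plan that is to be tried on blinded data and may be revised. These points limit the size of the problem but do not make the printed rules consistent.

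**Conclusion.** The point holds as a fault in the text of 5.8.4. Followed as printed, the rules give values that contradict Table 2-3 and the in-hospital column of Table 2-4, and differ more narrowly from the post-discharge column. The 18 h statement is wrong against the protocol schedules and the SAP's own windows.

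The impact is limited to one sensitivity analysis of a secondary endpoint. The primary analysis and the main estimate of clinical success at 48 h do not use these rules. The SAP expects partial missing data to be rare, so the likely effect is a few participants at 0.93 points each, assuming arms of 107.

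The 18 h gap applies to everyone who completes that visit, but that is not a misclassification rate: *no* is correct for anyone without the sign, and these variables are only covariates. They cannot carry the chemistry their names imply, and ACID_H18 can vary with respiratory distress, so the rule on constant covariates need not remove it.

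**What to change.** In SAP 5.8.4:

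1. Replace the three missing-item rules with a reference to Tables 2-3 and 2-4, and state that those tables take precedence and are applied first.
2. If AE or renal-replacement evidence is kept as a fallback, count any event ongoing at the visit, whatever its start day.
3. Remove Hour 18 from the list of lactate and creatinine assessments.
4. Drop REN_H18 from the models and replace ACID_H18 with respiratory distress at 18 h.

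The cost is a few lines of SAP wording and changes to two variables in the example code. No data collection, sample size or main analysis changes.
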